## **AIM 2**

### **III.A2. Aim 2 Research Design**

**Aim 2: Characterize HPHC and sugars yield in mainstream smoke generated from the four WP tobaccos characterized under Aim 1 using machine smoking of the RWP2, and a standardized WP puffing regimen.** Aim 2 will focus on quantifying the yields of toxicants in the mainstream smoke from the four WP tobaccos.

### **III.B2. Aim 2 Sample**

There are no human participants planned for Aim 2. Aliquots of the four tobacco preparations will be machine smoked and subsequent emissions will be collected/quantified for the toxicants of interest.

### **III.C2. Aim 2 Measurement/Instrumentation**

Nicotine, sugars, glycerol, carbonyls, and semivolatile furans, as shown in Table III.3, will be quantified in the mainstream WP tobacco smoke for the four tobaccos. Additional sets of machine smoking will be individually conducted for each tobacco batch, the gases will be collected as their derivatives in impingers and bulk particles will be collected on glass fiber filters located at the mouth-end of the WP hose, and the resulting impinger solutions and filters will be extracted and analyzed according to the methods described in Aim 1.

### **III.D2. Aim 2 Detailed Study Procedures**

Generation of WP Mainstream Smoke. The four tobacco preparations will be machine-smoked using a research-grade waterpipe, a calibrated smoking machine (Shisha Smoker, Borgwaldt), and an accepted standardized puffing regimen based on subjects smoking a popular flavored tobacco using the RWP in a laboratory environment. Particles and organic chemicals will be characterized and collected at the mouth-end of the WP hose.

Determination of HPHCs in Mainstream WP Tobacco Smoke. Total particulate matter and the HPHC content of the volatile and semivolatile fractions of the mainstream WP tobacco smoke will be characterized. Selected HPHCs and other toxicants are shown, along with reported WP smoke yields and health effects, in Table II.3. Machine smoking will be conducted and total particulate matter will be collected at the mouth end of the WP hose. Particle samples will be chemically extracted and analyzed for the target semi-volatile HPHCs using GC/MS and LC-MS/MS. Gas phase HPHCs will be collected in impingers and quantified as their DNPH derivatives.

### AIM 3

#### III.A3. Aim 3 Research Design

**Aim 3: Determine how WP tobacco content impacts puffing behaviors, CO biomarker, pulmonary function, nicotine uptake, and perceived sensory attributes and appeal of WP smoking.** Aim 3 will focus on using a group of established adult and young adult WP smokers, a cross-over study design, CO and nicotine biomarkers, spirometry, cutting edge psychophysical measurement tools, and risk perception instruments to map the relationship between sensory experiences and preferences of sweetness and flavor to specific additive content in WP tobacco that affect these experiences, preferences, acute health effects, and toxicant exposures.

*Table III.3. Selected compounds for chemical characterization.*

Compound	Mainstream Smoke Yield 		Reason for Selection
	Waterpipe	Cigarette	
Nicotine, TPM			
Nicotine (total), mg	0.01 – 9.29	0.1 – 3	Major addictive constituent
Total particulate matter, mg	242 – 2,350	1 – 27	Cardiovascular, pulmonary toxicant
Humectants, mg			
Glycerol	423	1.4 – 2.1 	Pulmonary toxicants, potential for carcinogenic
Propylene glycol	211	0.3 – 0.6 	degradation products
Semivolatile Furans, µg			
5-(Hydroxymethyl)-2-furaldehyde (HMF)	2,420 – 62,300	1.3 – 7.4	Potential for genotoxic and mutagenic metabolites in the lung
Furfuryl alcohol (FFA)	55.7 – 552	18 – 65	Nasal, kidney carcinogen; potential for genotoxic and mutagenic metabolites in the lung
2-Furoic acid (2-FA)	32.0 – 401	na	Pulmonary toxicant
Furfural (2F)	29.6 – 206	0.71 – 27.5	Potential human carcinogen; data gap
2-Furyl methyl ketone (2-FMK)	4.77 – 12.5	na	Pulmonary toxicant; data gap
5-Methyl-2-furaldehyde (5-M2F)	4.62 – 215	na	Pulmonary toxicant; data gap
Carbonyl Compounds, µg			
Acetaldehyde	120 – 2,520	0.01	Nasal mucosa, laryngeal carcinomas; enhances nicotine's addictiveness
Acetone	20.2 – 118	506 – 773 	Pulmonary toxicant
Acrolein	10.1 – 892	60 – 240	Lung carcinomas; pulmonary toxicant
Benzaldehyde	<0.34	0.4 – 6.4 	Pulmonary toxicant
Butyraldehyde	10.9 – 70.6	5.5 – 51.2 	Respiratory and cardiovascular toxicant
Formaldehyde	36 – 360	0.02	Nasal sinus, nasopharyngeal carcinoma, leukemia
Propionaldehyde	5.71 – 403	48.4	Pulmonary and cardiovascular toxicant

na = data gap, data not available; compounds in blue shaded rows are classified as HPHCs; compounds in orange shaded rows are proposed as additions to the HPHC list.

### III.B3. Aim 3 Sample

We will recruit a total of 60 healthy adult men and women with the goal of having complete data sets for 50 participants. Participants will meet the eligibility criteria shown in Table III.4. Established waterpipe smokers will be recruited from advertisements

*Table III.4. Participant inclusion and exclusion criteria.*

Inclusion	Justification for Inclusion
Sufficient understanding of consent form and study procedures	Necessary to ensure that participants are adequately informed about the study
Age 21-50 years old	Legally of age to purchase, use, and possess tobacco and provide informed consent
Experienced WP smokers defined as having smoked a WP at least 3 times per month in the last month	To assure that participants are experienced WP smokers, and increase the probability of subjects being able to comfortably smoke
Willing/able to abstain from nicotine product use for at least 12 hours prior to the laboratory visits	Necessary to normalize participants' willingness to smoke WP across visits
Willing to attend four laboratory sessions at the same time of day lasting approximately 3 h each	Necessary to complete all testing sessions and provide adequate power for data analysis
Read and speak English.	To ensure that participants are adequately informed about the study and can follow the
Exclusion	Justification for Exclusion
Evident intoxication on any visit	Intoxication would interfere with informed consent and study procedures
Exhaled breath CO > 10 ppm	Indicates recent combustible tobacco use.
Pregnancy (known or suspected), trying to become pregnant, breastfeeding, unwillingness to use contraception for the duration of the study.	Unethical to enroll pregnant or breastfeeding women for smoking research
Significant smoking-related disease (by history)	Unethical to enroll subjects with tobacco-related diseases
Any of the following in the past 30 days (self-report): 
 
• Uncontrolled asthma or asthma that is worse than usual.
 
• Severe respiratory allergies, such as wheezing, coughing, shortness of breath when exposed to known allergens.
 
• Acute upper or lower respiratory illnesses like the flu, common cold, or pneumonia.
 
• Any other serious lung infection or disease, such as tuberculosis, cystic fibrosis, or lung cancer.
 
• Hospitalization for difficulty breathing
 
	Unethical to enroll participants with significant pulmonary dysfunction or communicable disease
Currently engaging in a WP tobacco smoking quit attempt	Unethical to interfere with tobacco cessation

in college and community newspapers and through a variety of media outlets and the internet, including Study Search, as well as community events. Additionally, we will place flyers in WP cafés, and stores that cater to WP smokers, such as head shops and ethnic grocery stores.

Participants from other studies who have agreed to be contacted regarding other study opportunities will also be contacted. Staff from those studies will prepare contact letters/emails and call participants on behalf of this study. Participants interested will be referred to this study for screening. Advertisements will direct interested potential participants to complete a secure, online screener. Participants will access the screening questionnaire using a public survey link generated by REDCap. Information regarding eligibility and the participants' email addresses and phone numbers will be uploaded into a secure database. Potential participants will then be further screened by phone. Further assessment will be completed in person in a private setting. We will facilitate visits by offering weekend appointments and using additional retention strategies (e.g., reminder calls/texts/emails) that have been successfully used in the past for WP studies of similar size, crossover design, and subject burden.

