### II.2. How Do We Codify Harm?

The U.S. Food and Drug Administration (FDA), through the Family Smoking Prevention & Tobacco Control Act, classifies harm from tobacco products in terms of the chemical constituents that can be inhaled, ingested, or absorbed into the bodies of users. These harmful and potentially harmful constituents (HPHCs) have been measured in WP tobacco smoke, and thus have the potential to cause direct harm via delivery of carcinogens, pulmonary, cardiovascular and developmental toxicants, and addictive chemicals to the body, or indirect harm by facilitating tobacco initiation, increasing progression to cigarette smoking, impeding cessation of cigarette smoking, and/or increasing the intensity of tobacco product use.

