information and keep it confidential and anonymous through the use of IDs only and not personally identifying information.

De-identified, coded participant data from the general version of the Labeled Magnitude Scale (gLMS) and the Labeled Hedonic Scale (LHS) will be analyzed by [name], Associate Professor, Department of Food Science and Technology, Oregon State University. [name] will receive all scale ratings, matched with participant identification codes, date of participant laboratory visit, period data was collected (e.g., pre-smoking, post-smoking, etc.) and select demographic and tobacco use history data such as sex, age, and how many cigarettes smoked per day. All data sent to [name] will be stripped of participant identifying information.

During an ongoing virus pandemic (such as COVID-19), we will follow strict safety procedures to reduce risk of spread of the disease among the participants and staff. Depending on currently recommended guidelines, these procedures may entail:

- Collecting data on forehead temperature and assessing symptoms of viral infection at each visit
- Wearing personal protective equipment and sanitizing hands
- Routine cleaning of surfaces and equipment
- Implementing physical distancing

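### The quit-attempt exclusion in Table III.4 covers waterpipe only, while its stated reason covers tobacco cessation in general

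*Combined protocol and SAP*

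**What the plan says.** The eligibility rules are in Table III.4 of Section III.B3, with each criterion set beside its justification. The only criterion on quitting excludes a person "Currently engaging in a WP tobacco smoking quit attempt". Its justification reads "Unethical to interfere with tobacco cessation".

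Three other parts of the protocol bear on it:

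- **Background, Section II.2.** The list of indirect harms includes "impeding cessation of cigarette smoking". The sentence is about constituents measured in waterpipe smoke and is worded as a potential for harm.
- **Data sharing, Section V.1.** The data sent to the collaborator who analyses the sensory scales include "select demographic and tobacco use history data such as sex, age, and how many cigarettes smoked per day". Cigarette smoking among participants is thus foreseen.
- **Other tobacco-related criteria, Table III.4.** Exhaled CO above 10 ppm excludes, because it "Indicates recent combustible tobacco use". Participants must also be "Willing/able to abstain from nicotine product use for at least 12 hours prior to the laboratory visits".

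**The concern.** A criterion and its justification should protect the same people. Here the justification states a general principle about tobacco cessation, and the criterion applies it to one product. A person who is giving up cigarettes, or another nicotine product, but still smokes waterpipe often enough to qualify falls inside the principle and outside the rule.

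That person would then be asked to smoke nicotine-containing waterpipe tobacco freely, for up to 60 minutes, at four visits. Section V.2 says participants gain no direct benefit. At stake is consistency with an ethical limit that the protocol has set for itself, for a group that its own background section treats as potentially vulnerable.

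**Working it through.** The protocol gives no figure on this point to reproduce. The check compares the scope of the texts and asks whether anything else closes the gap.

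**1. Criterion against justification (Table III.4, same row).**
- Criterion: a current quit attempt for waterpipe tobacco.
- Justification: not interfering with tobacco cessation, with no product named.
- Result: the criterion is narrower than its reason. This follows from the row alone.

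**2. Can the people left uncovered be enrolled?**
- The inclusion criteria ask for age 21 to 50, waterpipe smoking at least 3 times in the last month, and willingness to abstain from nicotine before visits. None excludes cigarette smokers.
- The remaining exclusions concern intoxication, CO, pregnancy and related matters, smoking-related disease, and recent respiratory illness. None concerns cigarette use as such.
- Section V.1 lists "how many cigarettes smoked per day" among participant data. This supports the eligibility of co-users. It says nothing about their number.
- Result: yes.

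**3. Would another criterion detect a cigarette quit attempt?**
- The CO limit picks up recent smoking. A person who has stopped or cut down on cigarettes is more likely to pass it than a continuing smoker.
- The abstinence requirement (12 hours in Table III.4, at least 8 hours in Section IV; that difference is a separate matter) asks for short abstinence before a visit. A person who is quitting meets it easily.
- The monitoring plan in Appendix D describes screening for pregnancy and for respiratory and cardiovascular disease. It does not mention cessation.
- The risk text in Section V.1 does not mention quit attempts.
- Result: no. The CO and abstinence checks tend to let such a person through.

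**4. How large is the added exposure?**
- Eligibility requires at least 3 waterpipe sessions in the last month. Taking a month as 30 days, that is 3 / 30 × 7 = 0.7 per week or more.
- The study asks for 4 sessions at least a week apart, so at most 1 per week, over no less than 3 × 7 = 21 days from first to last.
- Result: study exposure is of the same order as the least use that qualifies. The protocol does not say whether the sessions replace usual smoking or add to it. The added exposure is at most 4 sessions per person.

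**5. How many participants?** The documents give neither the share of participants who use cigarettes or other nicotine products nor the share of those in a quit attempt. The number cannot be derived.

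**The case against.** The strongest reply is that a waterpipe-specific rule makes sense. A person quitting waterpipe would be handed the very product they are trying to give up. A person quitting cigarettes who still chooses to smoke waterpipe would be given something they already use at about the study's rate. On this view the general phrase in the justification column is shorthand, and widening the rule is a matter of preference.

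Part of this stands. The added exposure is modest, and a narrow rule could be defended. But the protocol does not offer that defence: the reason it prints names no product. Current waterpipe use also cannot settle the matter. Everyone eligible is a current waterpipe smoker, and the existing exclusion was still thought necessary.

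Three stronger readings are tempting, and the documents do not support them:

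- **That the protocol says waterpipe use impedes cigarette cessation.** Section II.2 says that smoke constituents "and thus have the potential to cause direct harm via delivery of carcinogens" and then lists indirect harms under the same wording. It describes a potential, and does not address four supervised sessions in established users.
- **That the narrow criterion biases the nicotine outcome.** Section IV assigns the order of tobaccos at random, Section VII.1 fits random subject effects, and nicotine boost is a difference within a visit. A change in cigarette use between visits is not tied systematically to any one tobacco. It can add within-person noise. Co-users who are not quitting can change their use too, so a wider exclusion would not remove that source.
- **That the screener asks only about waterpipe quitting.** Section III.B3 says that an online screener and a phone screen exist. Their questions are not reproduced, so they may or may not already cover other products.

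**Conclusion.** The mismatch holds on the text of Table III.4 alone, and no other section closes it. Staff who apply the table as written could enrol a person trying to quit cigarettes or another nicotine product, contrary to the reason printed beside the criterion.

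The practical size is unknown. Any count of affected participants would rest entirely on outside rates, and none is offered here. For each person affected, the added exposure is limited and incremental. Power, sample size and the planned comparisons are untouched.

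The conclusion assumes that the justification means what it says, namely tobacco in general. If the sponsor meant waterpipe only, the error is in the justification, and the two still need to be brought into line. Either way this is a minor point, worth making because it concerns who is protected and is cheap to correct.

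**What to change.** Reword the exclusion in Table III.4 so that it covers a current quit attempt for any tobacco or nicotine product, by self-report. Then check that the online and phone screening ask about it in those terms, and add or reword a question if they do not. Naming nicotine products goes one step beyond the literal justification, but it matches the abstinence criterion in the same table, which is already written in terms of nicotine product use.

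If the sponsor prefers to keep the waterpipe-only rule, the justification should be narrowed to match, with a sentence on why people quitting other products may be enrolled.

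The cost is one criterion and, at most, one screening question. The downside is a slightly higher screen-failure rate among co-users. Nothing in the analysis plan or the sample size section needs to change.

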### III.C3. Aim 3 Measurement/Instrumentation

Exhaled CO levels will be used to determine eligibility and CO boost (post- minus pre-smoking levels) from WP smoking using a handheld electrochemical sensor. The primary quantitative outcomes will be exhaled breath CO and plasma nicotine boost (post- subtracted from pre-smoking levels), puffing topography, spirometry measures [e.g., forced vital capacity (FVC), forced expiratory volume in 1 second (FEV1), FEV1/FVC, peak expiratory flow (PEF) and forced expiratory flow at 25-75% of FVC; and height and weight will also be assessed to calculate expected spirometry measures for participants. In addition, data will be collected electronically on participants' demographic characteristics, tobacco use history, nicotine dependence (Hooked on Nicotine Checklist, and Lebanese WP Dependence Scale), general harm and specific health risk perceptions, and subjective effects, including Direct Effects of Tobacco scale, Direct Effects of Nicotine scale, and Questionnaire for Urges to Smoke.

The primary qualitative outcomes will be verbal and non-verbal communication regarding the WP smoking experience and flavors perception. To determine the relative intensity of specific flavors, e.g., sweetness, we will use the general version of the Labeled Magnitude Scale (gLMS), to obtain data that would permit ratio comparisons of perceived sensation magnitudes. To assess the degree of liking or disliking of flavors, we will use the Labeled Hedonic Scale (LHS) to collect ratio-level data on the magnitude of liking and disliking of sensation. Other themes that emerge from the discussions will also be coded.

## IV. Detailed Study Procedures for the Human Study (Aim 3)

Study subjects will participate in a series of 4 laboratory sessions, each visit separated by at least a week, in which they smoke one of 4 tobacco preparations (blinded) using the RWP2, shown in Figure II.1, in a randomly assigned sequence, using the block randomization method. Smoking sessions will be carefully standardized: they will take place in a controlled setting, individual roomsdesignated for smoking research with sufficient ventilation rate at the Center for Tobacco

Research) within one hour of the same time-of-day after overnight nicotine abstinence ( $\geq 8$  hours, exhaled CO  $\leq 10$  ppm^173).

Research staff will light and add the charcoal and record tobacco and charcoal weights. The research-grade waterpipes will be prepared by the laboratory staff, and participants will smoke ad lib to satiation. Participants will be limited to one bowl (15 g) of tobacco and one quick-light charcoal (~10 g).

Prior to the start of the first laboratory visit, a research assistant will explain the study to the participant and answer any questions they may have. The participants will give an exhaled breath sample into the handheld CO monitor to determine if they are eligible to participate in the laboratory smoking session. If the participant's exhaled CO concentration is less than or equal to 10 ppm) they are deemed eligible to participate further, and will be asked to read the informed consent form. Once all participant questions have been answered, the participants will each be asked to sign their consent to participate in the study. Each female participant of child-bearing age will be asked to provide a urine sample for use in conjunction with a "dip-stick" pregnancy test to determine participation eligibility. Female participants with a negative urine pregnancy will be eligible to participate if they provide written agreement (via signing the consent form) to use reliable contraception throughout their participation in the study.

Each participant will then be asked to provide a pre-smoking blood sample by venipuncture. If the phlebotomist is unable to take a sufficient blood sample (10 mL) from the participant, the participant will be deemed ineligible to participate further in the study. Participants will then answer demographic and tobacco use questions.

After a successful blood sample collection, all participants will provide responses electronically to a series of questionnaires gathering information on nicotine dependence, and other subjective ratings. Participants will complete a practice session to learn how to record flavor perceptions. Height and weight will be measured for each participant.

Smoking will take place in a negative pressure room with a stable ventilation rate sufficient to keep ambient CO levels  $< 30$  ppmv. Participants will be seated in comfortable chairs designed for ease of blood collection by venipuncture. Using warm bottled water (body temperature), participants will clean their mouth and spit into a cup three times. Then, for 20 seconds, they will smell the unburned tobacco that they are assigned to smoke during that visit, and complete the questionnaire on their flavor perceptions. Participant lung function data will be collect using a handheld spirometry device. Exhaled breath CO levels will be collected for each participant just prior to the smoking session.

Participants will be encouraged to go to the bathroom prior to the start of the smoking session. The participant will be provided with a research-grade waterpipe that has been prepared with 15 g of one of the four tobacco preparations and one lit, quick-light charcoal. The participants will be instructed to smoke as they normally would or at a rate that is natural for them, through the hose/mouthpiece for up to 60 minutes. Puff topography parameters, including puff volume, duration, average and peak flow rate, and interpuff interval, will be measured continuously during the smoking session using the research-grade waterpipe. After the first 10 minutes of

smoking, and at the end of each smoking session, participants will be asked to rate the perceived intensities of relevant sensory attributes, including “sweetness,” “harshness,” “bitterness,” “smoothness,” and overall intensity, using the general version of the Labeled Magnitude Scale (gLMS). We will also collect data on liking/disliking by using the Labeled Hedonic Scale (LHS). If participants choose to smoke for 45 minutes, they will be asked to provide exhaled breath CO levels. If any participants breath CO levels exceed 50 ppmv, the smoking session will be stopped. Otherwise, participants may smoke *ad libitum* for as long as they choose, up to 60 total minutes. At the end of the smoking session, a second exhaled breath sample will be collected, and participants will then provide answers to questions regarding flavor perception. They will give a second blood sample and perform another lung function test, as before. Afterwards they will answer questions regarding nicotine dependence and their waterpipe smoking experience.

At the end of each smoking session, participants will respond to all subjective questionnaires including the gLMS and LHS. For each test tobacco, participants will be asked to rate perceived intensities of all relevant flavor qualities (i.e., sweetness, harshness, bitterness, smoothness, overall intensity, and specific flavor) as well as their liking/disliking on gLMS and LHS.

**Sensory Intensity and Hedonic Scales.** To determine the relative intensity including sweetness, harshness, and bitterness, and specific attributes of added flavors (e.g., apple) as well as the degree of liking/disliking for the four tobacco preparations, a psychophysical measurement technique will be employed to quantify the relationship between the tobacco flavors and their perceived intensity. Specifically, we will use the general version of the Labeled Magnitude Scale (gLMS), to obtain data that would permit ratio comparisons of perceived sensation magnitudes. The gLMS is a category-ratio scale bounded by “no sensation” at the bottom and “strongest imaginable sensation of any kind” at the top, with its intermediate intensity labels (weak, moderate, strong, and very strong) spaced logarithmically according to the empirically determined semantic magnitude. To assess the degree of liking or disliking of flavors, we will use the Labeled Hedonic Scale (LHS) to collect ratio-level data on the magnitude of liking and disliking of sensation. The properties of LHS are similar to the properties of the gLMS where the bipolar gLMS has “neutral” at its midpoint with negative descriptors to the left bounded by “strongest imaginable displeasure of any kind,” and positive descriptors to the right bounded by “strongest imaginable pleasure of any kind.”

**Biological Sample Collection.** Exhaled breath CO (via handheld electrochemical cell) and whole blood will be collected before and immediately after the WP smoking sessions according to previously developed protocols. Exhaled CO will also be measured after 45 minutes of *ad libitum* smoking, should participants choose to smoke that long. If after smoking for 45 minutes, any participant’s exhaled breath is greater than 50 ppm, the smoking session will be stopped. Within one hour of collection, the blood will be separated using centrifugation (1200 xg for 15 minutes), and the plasma layer will be transferred into a cryotube and stored at -80 °C until analysis for nicotine according to validated methods using LC-MS/MS.

**Spirometry.** Before and after smoking at each clinic visit, subjects will be asked to take a deep breath and then instructed to exhale forcefully into a handheld spirometer [NDD EasyOne Air Spirometer (NDD Medical Technologies, Andover, MA), or similar spirometer] according to American Thoracic Society Guidelines. This maneuver will be repeated up to 5 times in order to

ensure reproducible results. This non-invasive procedure will take up to 15 minutes to perform. Participants' height and weight will also be measured to calculate their expected spirometry measures as thresholds to use for determining potential impairment in lung function.

Safe Departure and Remuneration. At the end of each clinic session, research assistants will assess each of the participants for safe departure using a standardized checklist. An example checklist is provided in Appendix C. Visits 2-4 will be similar to the first visit, but the tobacco and use history data collection and the urine pregnancy test (women only) will not be repeated. Participants will receive \$50 for each laboratory visit and a bonus payment of \$50 for completing all four visits, for a total of \$250 at the conclusion of the last laboratory visit.

